Week	-10 to -4	-4 to -2	BSL	1	2	3	4	5	6	7	8	12	16	17	18	19	20	F24
Adverse events/SAEs (if applicable, including injection site reactions) ⁷	X																	
NSAID intake reported in eCRF		Χ	Х	Х	Х	Х	Х											X
Provide NSAID Diary to patient and instruct patient							Х				Х	х	Х					
NSAID intake captured in patient diary								х	х	Х	Х	х	Х	х	Х	х	Х	
Check NSAID diary									Х		Х	Х	Χ				Χ	
Patient's global assessment of disease activity (VAS)			x	х	X		x		x		X	X	X				X	х
Patient's assessment of back pain intensity (VAS)			х	х	х		х		Х		Х	х	Х				Х	х
BASFI			Х	Х	Х		Х		Х		Х	Х	Х				Х	Х

	Scree	ning ¹																
	Screening Visit 1	Screening Visit 2		Treatment 1										Follow Up				
Week	-10 to -4	-4 to -2	BSL	1	2	3	4	5	6	7	8	12	16	17	18	19	20	F24
BASDAI			Х	Х	Х		Х		Х		Х	Х	Х				Х	Х
Spinal mobility (BASMI Linear + chest expansion)			х		Х		х				х	х	х				Х	
SF-36			Х				Х					Х					Х	
ASAS Health Index			Х				Х					Х					Х	
Erythrocyte Sedimentation Rate (ESR)		Х	х		Х		х				Х	х	х				Х	х
High sensitivity C-reactive protein (hsCRP)		Х	х		Х		Х				х	х	х				Х	х
HLA-B27			Х															

¹ If the patient's washout period ≤ 4 weeks, Screening visit 1 (SV1) and Screening visit 2 (SV2) can be performed on the same day.

² Eligibility and relevant medical history assessments are conducted at SV1, SV2 and Baseline (BSL) / Day 1'. The data for all three visits should be recorded on the corresponding eCRFs available at SV1.

³ The following eCRFs are to be completed: AS Disease background eCRF, Modified New York criteria for AS eCRF

⁴ These assessments are source documentation only and will not be entered into the eCRF.

⁵ The PPD skin test can be performed at any time during the Screening period, but it must be read within 72 hours and before randomization.

	Scree	ening ¹																
	Screening Visit 1	Screening Visit 2					Treat	tment	:1					Tre	eatment	2		Follow Up
Week	-10 to -4	-4 to -2	BSL	1	2	3	4	5	6	7	8	12	16	17	18	19	20	F24

⁶ A chest X-ray or MRI is required if it was not performed and evaluated within 3 months prior to Screening. The X-ray should be performed after it is certain the patient meets inclusion/exclusion criteria in order to minimize unnecessary exposure to radiation. The X-ray may be replaced by an MRI assessment.

⁷ AEs/SAEs occurring after the patient has signed the informed consent must be captured on the appropriate eCRF page. SAEs must be recorded from signing of informed consent, AEs must be captured from the BSL visit on.

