13.4.1 Analysis and report of NSAID intake during clinical trials/studies

1. As soon as the information contained in Table 13-4 is available (eg, name, mean dose, number of days of intake during a period of time), the recommendation is to analyse/report the data in terms of NSAID equivalent dose in mg/day on a 0–100 scale. The 150 mg equivalent diclofenac is set to 100. When the exact number of days with NSAID intake is not known (usually when the interval of time between 2 visits exceeds 2 weeks), it is recommended to refer to the semi-quantitative estimation summarised in Table 13-4. In this case, a score of 7/7 is proposed for the answer 'every day', 6/7 for >5 days/week, 4/7 for >3 to ≤5 days/week, 2 for >1 to ≤3 days/ week, 0.5 for ≤1 day/week and 0 if the patient did not take any NSAID during the study period (Dougados et al 2011).

The general formula for the calculation is:

(equivalent NSAID score) × (days of intake during period of interest) × (days per week)/(period of interest in days)

 $^{^{\}mathrm{a}}$ Elevated ALT/AST > 3 × ULN and TBL > 2 × ULN but without notable increase in ALP to > 2 × ULN

Page 73

For example, if during a period of interest (between 2 visits) of 6 months, the patient has taken piroxicam 20 mg during 4 months and if during this 4-month period he has taken piroxicam 3–5 days per week the calculation is as follows:

100 (20 mg piroxicam score) \times 120 (4 months) \times 4/7 (3–5 days/week)/180 (6 months) = 38.1

If the patient has used 10 mg piroxicam during the remaining 2 months on 2 days a week, the NSAID score for this period is:

50 (10 mg piroxicam score) \times 60 (2 months) \times 2/7 (1–3 days/week)/180 (6 months) = 4.8 In this example the total score for the 6 month period is 42.9 (38.1 plus 4.8).

Table 13-4 ASAS recommendations for the approach to collection of NSAID intake for use in clinical trials/epidemiological studies of spondyloarthritis

NSAID intake si	nce the last visit	Yes □	No □	
NSAID name	Average daily intake	Days with intake	Starting date	Ending date
	III mg	<pre> <1 day/week</pre>	 	IIIIIII Ongoing

- 27. When the name and the dose of the NSAID intake are not available but the number of days with NSAID intake is available, the recommendation is to present the results as the percentage days with at least NSAID intake during a period of time.

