### 5.5.7 ASAS-NSAID Score

The recommendations by ASAS (Dougados 2010) will be used to score each patient's NSAID use during specific time periods. The components that go into the calculation of the score is the type of NSAID, average daily dose, length in days of the time period of interest and the number of days with NSAID intake within the time period of interest. The final score should be between 0 and 100 but can in rare cases be larger than 100.

The scoring of NSAIDs is described below.

Score	Intake
0	No intake
100	150 mg diclofenac, 600 mg etodolac, 150 mg indometacin, 20 mg piroxicam, 1000 mg naproxen, 90 mg etoricoxib, 200 mg ketoprofen, 20 mg tenoxicam, 200 mg aceclofenac, 200 mg flurbiprofen, 15 mg meloxicam, 400 mg celecoxib, 2400 mg ibuprofen, 400 mg phenylbutazone.

The CRF provided dose information will be handled as follows:

- Doses > maximum dose will be scored as > 100
- Missing doses will be scored with maximum daily dose for the current NSAID (i.e. score of 100)

Drug start and end dates are needed in order to know the number of days an NSAID was prescribed. In case they are missing, the following rules will be used:

- Missing start dates will assume the start date of medication is Day -28 (i.e. prior to start of study drug)
- Missing end dates will assume the end date of medication is the patient's last day in the Study

- If the study drug is ongoing when the patient discontinues then the drug end date will be equal to the day of discontinuation. The period end date will also end on the day of discontinuation

The table below presents the score associated with the dosing frequency as specified by the ASAS definition and how the different database entries will be categorized. The frequency was not consistently specified in the ASAS publication, the below categorization was selected.

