**Table 5-2 Mapping of dosing frequency to NSAID score**

Frequency	Scores	Database entry
Patient did not take any NSAID during the period of interest	0/7	
<1 day/week	0.5/7	Q2W, MISSING, PRN, UNK, ASNEEDED, QM, Q4W, Q3W
≥1 – <3 days/week	2/7	Q1W, WEEKLY, BIW
≥3 – <5 days/week	4/7	TIW, QIW
≥5 – <7 days/week	6/7	
Everyday	7/7	TID, BID, DAILY, Q24H, QID, QD
Note: Q2W=every 2 weeks, PRN=as needed, UNK=unknown, Q1W=one a week, BIW=twice a week, TIW=three times a week, TID=three times a day, BID=twice a day, QIW= four times a week, Q24H=QID=QD=one a day, QM=one a month; Q4W=one every 4 weeks; Q3W=one every 3 weeks.		

To calculate the NSAID cumulative score the following formula will be used for each NSAID being taken:

$100 * (\text{Daily dose} / \text{pre-specified max dose}) * \text{frequency score} * (\text{min}(\text{medication end date, period end date}) - \text{max}(\text{medication start date, period start date}) + 1 = \text{range of days patient used the medication}) / \text{number of days the patient was in the period.}$

In case a patient takes more than one type of NSAID, changes the dose or the frequency of NSAID during the period of interest, additional scores will be calculated for each new combination and the final score for that patient is the sum of all scores.

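### SAP 5.5.7 carries every undated NSAID record to the last study day and sums all records, so a taper can be scored as an increase and a stop as no change

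*SAP*

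**What the plan says.** SAP 5.5.7 scores each NSAID record as dose relative to a reference maximum, times a frequency score, times the share of the period covered. Four rules matter here.

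- **Blank end date:** "Missing end dates will assume the end date of medication is" the patient's last study day. The only mention of an ongoing drug in this section concerns patients who discontinue.
- **Days counted:** a record is cut off only at the earlier of "medication end date, period end date". The start of a later record of the same drug does not close it.
- **Several records:** when the NSAID, its dose or its frequency changes, "additional scores will be calculated for each new combination and the final score for that patient is the sum of all scores". Totals above 100 are allowed, although described as rare.
- **Blank dose:** "Missing doses will be scored with maximum daily dose for the current NSAID", that is, a score of 100.

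SAP 5.1.3 has a separate rule for partial end dates of concomitant medication that is not ongoing: end of month if the day is missing, or 31 December if the month is missing, in each case no later than the completion or discontinuation visit. The SAP does not say whether 5.1.3 or 5.5.7 governs NSAID records.

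Protocol 3.1 advises all patients to taper or stop NSAIDs from Week 4 to Week 20, preferably in steps. After Week 4, Protocol Table 6-1 has "NSAID intake captured in patient diary". Protocol 5.5.7 has the changes checked and transferred to the eCRF at scheduled visits. The end-date rule does not use the diary.

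**The concern.** In most trials, carrying an undated concomitant medication to the end of the study does little harm. Here the endpoint is the reduction in that medication. The rule is right for an NSAID that is still being taken. It is wrong for one that was reduced or stopped, and that is the effect under test.

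The change in ASAS-NSAID score is H2, the first test after the primary, and also H7 and H8. Under the testing strategy in SAP 2.7.2, failure of H2 makes H3 to H11 exploratory. SAP 2.7.3 specifies nothing for missing NSAID data and no sensitivity analysis of these imputations.

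The blank-dose rule leans the same way. It assigns the maximum, although entry is allowed from 50% of the highest recommended dose and doses are meant to fall after Week 4.

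**Working it through.** **1. The plan's own figures.** Protocol 9.7 assumes reductions of 63.9 and 36.6 (difference 27.3), SD 40, and states more than 90% power. I use power = Φ(difference / (SD × √(1/n₁ + 1/n₂)) − 1.96).

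- 62 per arm: 27.3 / (40 × √(2/62)) = 3.80, so power is 96.7%. The statement reproduces.
- Pooled, about 127 vs 63 from 190 patients at 1:1:1: 99.3%.
- The worked score in Protocol 13.4.1 also reproduces: 100 × 120 × (4/7)/180 + 50 × 60 × (2/7)/180 = 38.1 + 4.8 = 42.9.

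**2. One patient under the SAP formula.** Diclofenac 150 mg daily at baseline scores 100. The change occurs on Day 43. The SAP does not fix the length of the Week 12 scoring period, so I assume Days 58–85. The old record has no end date.

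| After Day 43 | True score (change) | SAP 5.5.7 score (change) |
|---|---|---|
| 75 mg daily | 50 (−50) | 100 + 50 = 150 (+50) |
| 75 mg twice weekly (2/7) | 14.3 (−85.7) | 114.3 (+14.3) |
| 150 mg as needed (0.5/7) | 7.1 (−92.9) | 107.1 (+7.1) |
| Stopped, no later record | 0 (−100) | 100 (0) |

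Each affected score is too high by 100, the full score of the old record. Other timings give the same pattern:

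- Change to 75 mg daily inside the period, on Day 71: true (100 × 13 + 50 × 15)/28 = 73.2; scored 100 + 50 × 15/28 = 126.8.
- Scoring over Days 29–85, change on Day 43: 62.3 is scored 137.7; a full stop, truly 24.6, is scored 100.

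**3. Blank dose.** For 75 mg daily with the dose missing, the score is 100 and the true value is 50. This needs a recorded daily frequency. SAP Table 5-2 maps a missing frequency to 0.5/7, so a record lacking both scores 100 × 0.5/7 = 7.1.

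**4. Trial level, illustrative only.** Neither document gives a rate of missing end dates.

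*Mild scenario: 10% of each arm's reductions are scored as zero.* The reductions become 57.5 and 32.9, with difference 27.3 × 0.9 = 24.6. At 62 per arm, power is 92.8% with SD 40, or 91.5% with SD 41.0 (allowing for the mixture). Pooled power is 97.9% with SD 40.

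*Harsher scenario: an error of +100 in a fraction m of patients who reduce.* Let q₁ and q₀ be m times the share who reduce on secukinumab and placebo. The difference is 27.3 − 100(q₁ − q₀). The SD is √(40² + q(1 − q) × 100²), with q = (2q₁ + q₀)/3. For example, with m = 10% and shares of 90% and 60%, the difference is 27.3 − 3.0 = 24.3 and the SD is √(1600 + 736) = 48.3.

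| Share who reduce (secukinumab / placebo) | m | Difference | Power, 62 per arm | Power, pooled |
|---|---|---|---|---|
| 80–90% / 50–60% | 5% | 25.8 | about 90% | 96–97% |
| same | 10% | 24.3 | 80–81% | 90–91% |
| same | 20% | 21.3 | 59–61% | 72–74% |
| 80% / 80% | 5% | 27.3 | 92.7% | 97.8% |
| same | 10% | 27.3 | 88.2% | 95.6% |
| same | 20% | 27.3 | 80.0% | 90.4% |

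With equal shares the difference is unbiased and only the variance grows.

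**The case against.** The strongest defence is that few records may be affected. The diary is kept daily, checked at Weeks 6, 8, 12, 16 and 20, transferred to the eCRF and subject to validation checks and queries (Protocol 8.2 and 8.3). The recommended collection form in Protocol Table 13-4 has an ongoing option beside the end date. Dates still blank at lock may mostly belong to drugs that really were ongoing, where the rule is right. The eCRF layout is not shown, so it is also an inference that each taper step creates a new record. This stands, and it limits what can be said about size.

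SAP 5.1.3 may also govern partial dates. If only the day is missing, the overlap would be limited to about a month. This stands too, but 5.1.3 does not close an old record when a new one starts, and precedence is unstated.

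Finally, a bias against secukinumab is conservative for a superiority test. That is true if secukinumab patients reduce more often, which is plausible but assumed, since all arms are advised to taper. It does not justify a rule that gives a patient who halved the dose a positive change.

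Three stronger readings are tempting, and the documents do not support them:

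- *Every stopped NSAID becomes an increase.* The sign reverses only if there is a later record. A stop without one scores as no change.
- *The stated power is lost.* In the mild scenario it stays above 90%. Larger losses rest on error sizes and shares found in neither document.
- *The blank-dose rule contradicts Protocol 13.4.1, so SAP section 4 wrongly reports no changes.* The protocol item begins "When the name and the dose of the NSAID intake are not available but the number of days with NSAID intake is available". It covers name and dose both being unknown and recommends reporting the percentage of days. It is not a rule for one blank dose of a known NSAID.

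**Conclusion.** The concern holds for individual scores. Read as written, SAP 5.5.7 counts an undated record together with its lower-dose or lower-frequency successor, and no other section prevents this. In the diclofenac example the error is 100 points per affected patient, against a planned arm difference of 27.3. A true −50 is scored +50, and a true −100 with no later record is scored 0.

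The effect on the trial is unknown and may be small, because it depends on how many end dates are missing at lock. If patients who reduce are more common on secukinumab, the bias is against showing NSAID sparing in H2, H7 and H8. If they are equally common in both arms, the loss is in precision. The plan should be changed because the rule gives a wrong result where the trial may hold better information.

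**What to change.** Amend SAP 5.5.7 before database lock.

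1. **Missing end date.** Use the last study day only for records flagged ongoing or with no contrary information.
   - Where a later record of the same NSAID at a different dose or frequency exists, end the undated record the day before that record starts.
   - Where completed diary pages positively record no intake, end it at the last recorded intake day. Do not treat missing pages as no intake, because that would overstate sparing.
2. **Concurrent use.** Keep summing genuinely concurrent different NSAIDs and on-demand top-ups, which the protocol and the summing rule allow.
3. **Missing dose.** Use the patient's nearest recorded dose of the same NSAID, and the maximum only if there is none.
4. **Precedence.** State whether 5.5.7 or 5.1.3 governs partial dates of NSAID records.
5. **Reporting.** Give counts of imputed end dates and doses by arm, and run the current rule as a sensitivity analysis.

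The cost is SAP wording and some extra programming, with no new data. The downside is a somewhat less conservative imputation, which the sensitivity analysis makes visible.

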## 4 Change to protocol specified analyses

Not applicable.

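### SAP Table 5-2 closes the ASAS-NSAID frequency classes at the opposite end from the protocol text, so weekly and three-times-weekly intake match neither the protocol bands nor the known day count

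*SAP*

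**What the plan says.** **Protocol 13.4.1.** The frequency classes are a fallback: "When the exact number of days with NSAID intake is not known (usually when the interval of time between 2 visits exceeds 2 weeks". For that case the weights are 7/7 for daily use, then "6/7 for >5 days/week, 4/7 for >3 to ≤5 days/week, 2 for >1 to ≤3 days/ week, 0.5 for ≤1 day/week". Each class includes its upper limit. The last two weights are printed without the divisor; the worked example shows that 2 means 2/7, and I read 0.5 as 0.5/7 in the same way.

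**SAP 5.5.7 and Table 5-2.** After the remark "The frequency was not consistently specified in the ASAS publication, the below categorization was selected", the table sets these classes, each of which includes its lower limit:

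- below 1 day a week: 0.5/7 (includes PRN, as-needed and missing)
- 1 to below 3 days: 2/7 (Q1W, WEEKLY, BIW)
- 3 to below 5 days: 4/7 (TIW, QIW)
- 5 to below 7 days: 6/7 (no database code listed)
- every day: 7/7 (QD, BID, TID, QID and others)

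The note under the table reads in part "Q24H=QID=QD=one a day".

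**SAP section 4**, on changes to the protocol's analyses, reads "Not applicable".

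**The concern.** Moving the closed end of each class shifts exactly 1, 3 and 5 days a week up one class. Codes such as Q1W and TIW sit exactly on those limits. Their days per week are also known, so no band is needed for them. Under Table 5-2 a weekly user scores the same as a twice-weekly user, and a three-times-weekly user the same as a four-times-weekly user.

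The change from baseline in this score is the endpoint of H2 (pooled), H7 (delayed tapering) and H8 (early tapering). H2 comes second in the testing order, so if it fails, H3 to H11 become exploratory. Daily use scores 7/7 under both documents. The affected codes should therefore arise mainly after Week 4, when patients taper and the endpoint is measured.

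**Working it through.** **1. Reproduce the protocol's example.** The score is the dose score × days of intake × frequency weight ÷ days in the period.

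- First NSAID spell: 100 × 120 × (4/7) ÷ 180 = 38.1, as in "4/7 (3–5 days/week)/180 (6 months) = 38.1".
- Second spell: 50 × 60 × (2/7) ÷ 180 = 4.8, as in "2/7 (1–3 days/week)/180 (6 months) = 4.8".
- Total: 42.9, which agrees with the protocol.

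The band in the first spell runs from 3 to 5 days. A patient at exactly 5 days keeps 42.9 under the protocol text. Under the SAP limits the weight becomes 6/7 and the total is 100 × 120 × (6/7) ÷ 180 + 4.8 = 61.9.

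**2. Compare the weights.** Score at dose score 100 for the whole period = 100 × weight:

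| Days/week | Code listed in Table 5-2 | Protocol text | Exact days | SAP | SAP − protocol | SAP − exact |
|---|---|---|---|---|---|---|
| 1 | Q1W/WEEKLY | 7.1 | 14.3 | 28.6 | +21.4 | +14.3 |
| 2 | BIW | 28.6 | 28.6 | 28.6 | 0 | 0 |
| 3 | TIW | 28.6 | 42.9 | 57.1 | +28.6 | +14.3 |
| 4 | QIW | 57.1 | 57.1 | 57.1 | 0 | 0 |
| 5 | none | 57.1 | 71.4 | 85.7 | +28.6 | +14.3 |
| 6 | none | 85.7 | 85.7 | 85.7 | 0 | 0 |
| 7 | daily codes | 100 | 100 | 100 | 0 | 0 |

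**3. Scale by dose.** The gaps are proportional to dose. At half the maximum dose, the entry minimum in inclusion criterion 8, they are +10.7 (1 day) and +14.3 (3 or 5 days) against the protocol text, and +7.1 against exact days.

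**4. Possible effect on the comparison.** Protocol 9.7 assumes reductions of 63.9 and 36.6 with SD 40, a difference of 27.3. With 62 per arm the power is Φ(27.3 ÷ (40 × √(2/62)) − 1.96) = 97%, consistent with the stated figure above 90%. For the pooled test with about 127 against 63 (190 patients, 2:1) it is 99%.

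The documents do not say how many patients will carry an affected code. Suppose that s is the excess share of such patients on secukinumab over placebo, all at full dose and measured against the protocol bands. The difference then becomes 27.3 − s × (21.4 to 28.6):

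| Assumed s | Difference | Power, 62 vs 62 | Power, 127 vs 63 |
|---|---|---|---|
| 10 points | 24.4–25.2 | 93–94% | 98% |
| 20 points | 21.6–23.0 | 85–89% | 94–96% |
| 30 points | 18.7–20.9 | 74–83% | 86–92% |

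Measured against exact days, s = 20 points gives 27.3 − 0.2 × 14.3 = 24.4. If s is negative, the difference grows instead. The table illustrates scale; it does not predict the result.

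**5. QID.** Once a day and four times a day both fall in the daily row, so the weight is 7/7 under either reading.

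**The case against.** The case for leaving the table alone has four parts.

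- **The protocol has no single set of limits.** Its Table 13-4 appears to print the lowest class as below 1 day a week, which is the SAP's limit, and the example labels its classes 1–3 and 3–5 with shared ends. This stands: the protocol needs reconciling too. Table 13-4 is broken in the text available to me, so that sign should be checked in the original.
- **The choice is disclosed.** SAP 5.5.7 says openly that a categorization was selected. It does not say that this departs from the protocol text, and section 4 does not list it.
- **The protocol bands apply only when exact days are unknown.** Intake is recorded daily in the diary from Week 4. This stands, and makes 14.3 the fairer gap for known-day codes. It does not support Table 5-2, though. SAP 5.5.7 names days of intake as an input, yet its formula uses only a frequency weight and medication dates.
- **Few codes are affected.** Among listed codes, only Q1W/WEEKLY and TIW are. The 5-day case arises only if such a record is entered.

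Three stronger readings are tempting, and the documents do not support them. A reader might infer that everyone on 1, 3 or 5 days a week is scored 21 to 29 points too high. That is the gap at full dose for the whole period, measured against bands meant for unknown days.

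A reader might also infer that the NSAID-sparing effect is understated. All arms are advised to taper. If secukinumab patients stop altogether while placebo patients settle at three days a week, Table 5-2 inflates the placebo scores and the effect is overstated. On-demand use may be recorded as PRN, which scores only 0.5/7 and could understate intake.

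Finally, the QID note might suggest that 600 mg ibuprofen four times a day scores 600/2400 × 100 = 25 instead of 100. That requires a per-intake dose to be entered as the daily dose. The SAP names the average daily dose as its input, and protocol Table 13-4 collects average daily intake.

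**Conclusion.** The mismatch is real and should be corrected. For Q1W/WEEKLY and TIW, Table 5-2 gives weights that agree with neither the protocol text (0.5/7 and 2/7) nor the days that the codes state (1/7 and 3/7). The excess over exact days is 14.3 points at full dose for the whole period and 7.1 at half dose. Against the protocol bands it is 21.4 and 28.6, or 10.7 and 14.3 at half dose.

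These are per-patient figures and cannot be set directly against the assumed group difference of 27.3. The number of affected records and the net direction of any bias in H2, H7 and H8 are unknown. The conclusion rests on reading 0.5 as 0.5/7 and on the codes meaning what the table note says. The QID note is a separate labelling error with no effect on the frequency weight.

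**What to change.** - In Table 5-2, score codes with known days exactly: Q1W/WEEKLY 1/7, BIW 2/7, TIW 3/7, QIW 4/7.
- Use the diary's exact count of intake days wherever it is available, and say so in the formula. Keep bands for records without a day count.
- For banded answers, adopt one set of limits across the protocol 13.4.1 text, protocol Table 13-4 and SAP Table 5-2, and print the divisor of 7 on every weight.
- Replace the entry in SAP section 4 with a statement of any departure from the protocol text.
- Add a sensitivity analysis of H2, H7 and H8 with the protocol limits, and report by arm how many records carry an affected code.
- Correct the QID note to four times a day.

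The cost is SAP wording, a lookup table and one extra model run per hypothesis. The SAP's document history places it before database lock, so no new data are needed. Aligning the protocol appendix needs a short clarification there.
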